- Clinical status assessed using ordinal scale on Study Days 1, 3, 5, 8, 11, 15, 22, and 29;
- Change in clinical status using change in ordinal scale from Study Day 1 to Study Days 3, 5, 8, 11, 15, 22, and 29;
- Days of supplemental oxygen or worse (i.e., ordinal score of 5, 6, 7, 8) up to and including Study Day 29;
- Days of non-invasive ventilation/high-flow oxygen or worse (i.e., ordinal score of 6, 7, 8) up to and including Study Day 29;
- Whether a subject who has a baseline ordinal score of 5 requires new non-invasive oxygen use or worse (i.e., ordinal score of 6, 7, 8) during the study up to and including Study Day 29 (incidence);
- Days a subject who has a baseline ordinal score of 5 has an ordinal score of 6 or greater up to and including Study Day 29;
- Days of invasive mechanical ventilation/ECMO or worse (i.e., an ordinal score of 7 or 8) up to and including Study Day 29;
- Whether subject who has a baseline ordinal score of 5 or 6 requires new invasive ECMO use or worse (i.e., ordinal score of 7 or 8) during study up to and including Study Day 29 (incidence);
- Days a subject who has a baseline ordinal score of 5 or 6 has an ordinal score > 6 up to and including Study Day 29;
- Whether a subject is alive and without respiratory failure (ordinal score < 7) at Study Day 29;
- Time (days) to ventilation or death from Study Day 1 up to and including first 29 days of being on study.
- Days of hospitalization from date of admission up to and including Study Day 29.
- Values of C-reactive protein (CRP), ferritin, D-dimer, lactate dehydrogenase (LDH), and fibrinogen on Study Days 1, 3, 5, 8, and 11 (while hospitalized); and Study Days 15 and 29 (if attends in-person visit or still hospitalized).

Safety

- Whether a subject died from Day 1 up to and including Study Day 15.
- Whether a subject died from Day 1 up to and including Study Day 29.
- Whether a subject died from Day 1 up to and including Study Day 60.
- Time (days) to death from Study Day 1 up to and including Study Day 29.

- Whether a subject experienced at least one SAE up to and including Study Day 60.
- Whether a subject experienced at least one Grade 3 or Grade 4 AE up to and including Study Day 60.
- Episodes of early discontinuation or interruption of study product administration.

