2. Time to 2-points improvement by Day 60	Primary	
 Use the complete data for ordinal score to define time to improvement. Subjects whose last assessment in the study is prior to an observed improvement will be censored at the day of their last assessment. Subjects who complete follow-up but do not experience improvement will be censored at the day of their Study Day 60.

Endpoint	Analysis	Imputation Method
		
 Death prior to improvement will be considered not improved and censored at expected study Day 60.
	Subgroup	
 Repeat analysis for each subgroup using same imputation as primary analysis for this endpoint.
3. Clinical status assessed using ordinal scale on Study Days 1, 3, 5, 8, 11, 15, 22, and 29; Change in clinical status using change in ordinal scale from Study Day 1 to Study Days 3, 5, 8, 11, 15, 22 and 29.	Primary	
 Use complete data for ordinal score.
	Subgroup	
 Repeat analysis for each subgroup using same imputation as primary analysis for this endpoint.
4. Days of supplemental oxygen by Study Day 29;	Primary	
 If the subject's clinical status scale is 6 or above at the last observed assessment, then the subject will be considered to be on supplemental oxygen use through Day 29. The endpoint will be total days when assessments are available plus all imputed days following the last observed assessment. If the subject's clinical status is less than 6 at the last observed assessment, then the subject will be considered to not be on supplemental oxygen use for the remainder of follow-up. Thus, no additional imputed days will be added to the number of days recorded on available assessments.
	Subgroup	
 Repeat analysis for each subgroup using same imputation as primary analysis for this endpoint.

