5. Days of non-invasive ventilation/high-flow oxygen by Study Day 29;	Primary	
 If the subject's clinical status scale is 6 or above at the last observed assessment, then the subject will be considered to be on non-invasive ventilation/high-flow oxygen through Day 29. The endpoint will be total days when assessments are available plus all imputed days following the last observed assessment. If the subject's clinical status is less than 6 at the last observed assessment, then the subject will be considered to not be on non-invasive ventilation/high-flow oxygen for the remainder of follow-up. Thus, no additional imputed days will be added to the number of days recorded on available assessments.
	Subgroup	
 Repeat analysis for each subgroup using same imputation as primary analysis for this endpoint.
6. Incidence of new non-invasive oxygen use (clinical status > 5) during the study up to and including Study Day 29 for subject with baseline clinical status of 5	Primary	
 If the subject's clinical status scale is 6 or above at the last observed assessment, then the subject will be considered to be on non-invasive ventilation/high-flow oxygen through Day 29. The endpoint will be total days when assessments are available plus all imputed days following the last observed assessment. If the subject's clinical status is less than 6 at the last observed assessment, then the subject will be considered to not be on non-invasive ventilation/high-flow oxygen for the remainder of follow-up. Thus, no additional imputed days will be added to the number of days recorded on available assessments.
7. Days a subject who has a baseline clinical status of 5 has a clinical status > 5 up to and including Study Day 29;	Primary	
 Use complete data for ordinal score to define this endpoint.
	Subgroup	
 Use complete data for ordinal score to define this endpoint.

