8. Days of invasive mechanical ventilation/ECMO by Study Day 29;	Primary	
 If the subject's clinical status scale is 7 or above at the last observed assessment, then the subject will be considered to be on invasive mechanical ventilation/ECMO through Day 29. The endpoint will be total days when assessments are available plus all imputed days following the last observed assessment. If the subject's clinical status is less than 7 at the last observed assessment, then the subject will be considered to not be on invasive ventilation/ECMO for the remainder of follow-up. Thus, no additional imputed days will be added to the number of days recorded on available assessments.
	Subgroup	
 Repeat analysis for each subgroup using same imputation as primary analysis for this endpoint.

Endpoint	Analysis	Imputation Method
9. Incidence of new invasive ECMO use through study Day 29 for subjects with baseline clinical status of 5 or 6;	Primary	
 If the subject's clinical status scale is 7 or above at the last observed assessment, then the subject will be considered to be on invasive mechanical ventilation/ECMO through Day 29. The endpoint will be total days when assessments are available plus all imputed days following the last observed assessment. If the subject's clinical status is less than 7 at the last observed assessment, then the subject will be considered to not be on invasive ventilation/ECMO for the remainder of follow-up. Thus, no additional imputed days will be added to the number of days recorded on available assessments.
10. Days a subject who has a baseline clinical status of 5 or 6 has a clinical status > 6 up to and including Study Day 29;	Primary	
 Use complete data for ordinal score to define this endpoint.
	Subgroup	
 Repeat analysis for each subgroup using the complete dataset for ordinal score.

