The main analysis of the primary endpoint will be repeated using the ordinal score on Study Days 15 and 29 instead of Day 8 using complete data, adjusting for baseline severity and steroid use. The analysis will be repeated for baseline severity of disease, baseline steroid use, baseline use of emerging COVID-19 treatments, and duration of symptoms subgroups. Each subgroup will be considered separately, and the estimated treatment odds ratio from the proportional odds model with corresponding 95% and 80% confidence intervals and the p-value will be presented for each subgroup. A forest plot will be generated to display the overall treatment odds ratio and CI from each of the within-stratum analyses. Results for Day 15 will be presented in Table 17, Figure 4, and Figure 5 while results for Day 29 will be presented in Table 18, Figure 6, and Figure 7. These analyses will be repeated for the ITT population and results will be presented in Table 20 and Table 21. Odds ratios between the binary progression strata from the proportional odds model are reported in Table 24, Table 25, Table 26, Table 27 for mITT population and ITT population for Study Days 15 and 29.

Oxygenation

Oxygen days will be defined as the number of days where the ordinal score > 4 up to and including Study Day 29. The total number of days will be the sum of all reported days, regardless of whether the days occur consecutively or in disjoint intervals. For planned gaps between study days, the day of the qualifying Study Day and the days to the next planned Study Day will be included in the total number of days. The Post-Discharge Supplemental Oxygen CRF questions regarding days of oxygenation (including ECMO, invasive ventilation, non-invasive ventilation, high-flow oxygen devices, and all other oxygen delivery devices) will be used for any time period the subject is not hospitalized at the study hospital. See Section 6.5 for the plan for handling subjects who do not have data through Study Day 29 or die prior to Study Day 29.

Duration of oxygenation days will be summarized in a table using medians and quartiles by treatment (Table 36). Bee swarm plots of oxygen days by treatment will be generated (Figure 19).

Refer to Table 6 for a list of covariates and subgroup analyses for this endpoint. Refer to Table 7 for imputation methods to be applied to this endpoint.

Non-Invasive Ventilation/High-Flow Oxygen

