Non-invasive ventilation/high flow-oxygen days or worse will be defined as the number of days where the ordinal score is > 5 up to and including Study Day 29. The total number of days will be the sum of all reported days, regardless of whether the days occur consecutively or in disjoint intervals. For planned gaps between study days, the day of the qualifying Study Day and the days to the next planned Study Day will be included in the total number of days. The Post-Discharge Supplemental Oxygen CRF questions regarding days of non-invasive ventilation or high-flow oxygen will be used for any time period the subject is not hospitalized at the study hospital. See Section 6.5 for the plan for handling subjects who do not have data through Study Day 29 or die prior to Study Day 29.

Duration of non-invasive ventilation/high flow oxygen days or worse will be summarized in a table using medians and quartiles by treatment (Table 37). Bee swarm plots of non-invasive ventilation/high flow oxygen days by treatment will be generated (Figure 20).

The incidence and duration of new Non-Invasive Ventilation/High-Flow Oxygen use or worse will be analyzed by treatment (Table 40). The numerator will include only subjects in category 5 or below at enrollment who change to a category 6, 7, or 8. The denominator will only include subjects with an actual baseline ordinal score of 5 or below at enrollment. The number of subjects reporting new use of Non-Invasive Ventilation/High-Flow Oxygen and the incidence rate along with 95% and 80% CIs estimated using the Blaker method will be reported.

Refer to Table 6 for a list of covariates and subgroup analyses for this endpoint. Refer to Table 7 for imputation methods to be applied to this endpoint.

Invasive Mechanical Ventilation/ECMO

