Ventilator / ECMO days will be defined as the number of days where the ordinal score > 6 up to and including Study Day 29. The total number of days will be the sum of all reported days, regardless of whether the days occur consecutively or in disjoint intervals. For planned gaps between study days, the day of the qualifying Study Day and the days to the next planned Study Day will be included in the total number of days. The Post-Discharge Supplemental Oxygen CRF questions regarding days of ECMO or invasive ventilation will be used for any time period the subject is not hospitalized at the study hospital. See Section 6.5 for the plan for handling subjects who do not have data through Study Day 29 or die prior to Study Day 29.

Duration of Invasive Mechanical Ventilation/ECMO days will be summarized in a table using medians and quartiles by treatment (Table 38). Bee swarm plots of Invasive Mechanical Ventilation/ECMO days, and days hospitalized by treatment will be generated (Figure 21).

The incidence of new Invasive Mechanical Ventilation/ECMO use will be analyzed by treatment (Table 41). The numerator will only include subjects in category 6 or below at enrollment who change to a category 7 or 8. The denominator will include subjects with a baseline ordinal score of 6 or below. The number of subjects reporting new use of Invasive Mechanical Ventilation/ECMO and the incidence rate along with 95% and 80% CIs estimated using the Blaker method will be reported.

Refer to Table 6 for a list of covariates and subgroup analyses for this endpoint. Refer to Table 7 for imputation methods to be applied to this endpoint.

Proportion of Subjects Alive and Without Respiratory Failure at Study Day 29

The proportion of subjects alive and without respiratory failure at Study Day 29 will be defined as the proportion of subjects with an ordinal score < 7 at any time between Day 26 through Day 32 (Visit window for Study Day 29 Visit). The proportion of subjects with respiratory Failure or death at Day 29 will also be provided. These proportions will be presented by treatment along with 95% and 80% Blaker CIs. Treatment differences will be evaluated using a logistic regression and the p-value will be presented (Table 31).

Refer to Table 6 for a list of covariates and subgroup analyses for this endpoint. Refer to Table 7 for imputation methods to be applied to this endpoint.

Time to Mechanical Ventilation or Death up to and Including Day 29

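### Table 7 row 4 imputes a last score of 5 as off oxygen, although the oxygen-days endpoint counts score 5

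*SAP*

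**What the plan says.** The endpoint is defined consistently in three places in the SAP. Section 3.2 lists "Days of supplemental oxygen or worse (i.e., ordinal score of 5, 6, 7, 8) up to and including Study Day 29". Section 8.2.2 (Oxygenation) says "Oxygen days will be defined as the number of days where the ordinal score > 4 up to and including Study Day 29". Table 9 in Section 6.8 again uses scores above 4. On the scale in Section 3.2, score 5 is a hospitalized patient who needs new or increased supplemental oxygen.

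For subjects without data through Day 29, Section 8.2.2 refers to Section 6.5. There, Table 7 row 4 carries oxygen use forward to Day 29 only if the last score is 6 or above. For anyone whose "clinical status is less than 6 at the last observed assessment, then the subject will be considered to not be on supplemental oxygen use" the count stops at the last assessment.

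The neighbouring rows are built the same way:

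- Row 5 (non-invasive ventilation or high-flow oxygen): a subject whose "clinical status is less than 6 at the last observed assessment, then the subject will be considered to not be on non-invasive ventilation/high-flow oxygen" gets no further days. Section 8.2.2 defines that endpoint as "the number of days where the ordinal score is > 5 up to and including Study Day 29".
- Row 8 (invasive ventilation or ECMO): a subject whose "clinical status is less than 7 at the last observed assessment, then the subject will be considered to not be on invasive ventilation/ECMO" gets no further days. For ventilator/ECMO, Section 8.2.2 says "days will be defined as the number of days where the ordinal score > 6 up to and including Study Day 29".

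For time away from the study hospital, Section 8.2.2 adds that the post-discharge oxygen questions on the CRF "will be used for any time period the subject is not hospitalized at the study hospital".

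**The concern.** Row 4 assumes that a patient last seen in hospital on supplemental oxygen came off it at once, although the endpoint counts that state as an oxygen day. Its cut-off and sentence structure are those of row 5, where 6 is correct. No reason is given for using 6 in row 4, so it reads like a carry-over.

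Protocol Section 5.1 admits subjects at score 5, 6 or 7, so score 5 is an ordinary state at entry. Two subjects lost on the same day, one at score 5 and one at score 6, both on oxygen, would get very different totals. Table 6 repeats this endpoint by baseline ordinal score and Table 7 keeps the same imputation for subgroups, so the asymmetry also falls between displayed subgroups of Table 36.

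**Working it through.** **Cut-offs side by side.** For each score from 1 to 8, compare whether the endpoint counts it with whether Table 7 carries it forward.

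| Table 7 row | Endpoint counts | Carried to Day 29 if last score is | Scores that disagree |
|---|---|---|---|
| 4, supplemental oxygen | 5 to 8 | 6 to 8 | 5 |
| 5, non-invasive or high-flow | 6 to 8 | 6 to 8 | none |
| 8, invasive ventilation or ECMO | 7 to 8 | 7 to 8 | none |

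**Day counts.** Take a subject on oxygen every day, last assessed on Day k at score 5, who withdraws while in the study hospital. Row 4 gives k days. A cut-off of 5 gives 29. The difference is 29 − k: 28, 25, 21 and 14 days for k = 1, 4, 8 and 15. These are differences between two rules, not errors against the truth. They do not apply to every subject: someone transferred or discharged may gain days from the post-discharge oxygen form or from the Section 8.2.2 rule for planned gaps between visits.

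**Distance from a plausible truth.** The SAP gives no figure for this, so a model has to be assumed.

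- Input: Table 4 (Section 5) expects 17.1 + 8.8 + 24.2 + 3.5 = 53.6% of controls at score 5 to 8 on Day 8.
- Assumption: time to coming off oxygen is exponential, all eligible subjects are at score 5 to 7 on Day 1, and Day 8 is 7 days later.
- Mean: m = −7 / ln(0.536) = 11.22 days.
- Expected further oxygen days after Day k, up to Day 29: E = m × (1 − exp(−(29 − k)/m)).
- Row 4 adds no days, so it undercounts by E. The matched rule adds 29 − k days, so it overcounts by (29 − k) − E.

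For k = 1: exp(−28/11.22) = 0.536⁴ = 0.0825, so E = 11.22 × 0.9175 = 10.3 and the overcount is 28 − 10.3 = 17.7.

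The 53.6% includes ventilated (24.2%) and dead (3.5%) subjects, so it may be too high for subjects at score 5. The last two columns repeat the calculation with an assumed 40% still on oxygen after 7 days, which gives m = −7 / ln(0.40) = 7.64.

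| Last day k | Row 4 undercounts (53.6%) | Matched rule overcounts (53.6%) | Row 4 undercounts (40%) | Matched rule overcounts (40%) |
|---|---|---|---|---|
| 1 | 10.3 | 17.7 | 7.4 | 20.6 |
| 4 | 10.0 | 15.0 | 7.3 | 17.7 |
| 8 | 9.5 | 11.5 | 7.2 | 13.8 |
| 15 | 8.0 | 6.0 | 6.4 | 7.6 |

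For losses by Day 8 the current rule is closer per subject in both scenarios. At Day 15 the result depends on the assumed percentage.

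**The case against.** The strongest reply is that row 4 does not misclassify any observed day. Every day recorded at score 5 counts, and the rule governs only days nobody saw. Someone on low-flow oxygen may well come off it soon, so stopping the count is a defensible guess, and the table above shows that it is often the nearer one. This stands as far as it goes. It limits the point to an imputation rule that does not fit its endpoint. It does not explain why row 4 departs from rows 5 and 8, which carry the qualifying state forward, and the SAP does not present the choice as deliberate.

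A second objection is that a good-discharge exception in row 4 would itself differ from rows 5 and 8, which have none. That is true. The reason for it is that Section 8.2.1 treats the score as reflecting the previous 24 hours, so a patient just sent home can have a last score of 5, and the complete-data rules in Section 6.5.1 then assign score 2.

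A reader might also infer that the SAP settles on a second derivation of the same endpoint in optional Tables 44 and 45. The documents do not support that. The note to Table 44 points to complete data, but the pseudocode heading for that method in Section 6.8 refers to observed data. For Table 45, Section 6.8 takes p-values from each endpoint's primary analysis, while the table's footnote says complete data. The input is unclear, so these tables cannot serve as evidence.

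**Conclusion.** The inconsistency is certain as written: exactly one score, 5, is counted by the endpoint and dropped by the imputation, and nothing in the supplied documents repairs it. Its reach is small. It affects only subjects with no data after a last score of 5, and Section 6.5.1 expects little missing data after chart review. Oxygen days are an other-secondary endpoint summarized by medians and quartiles in Table 36. The primary and key secondary analyses do not use row 4. A stage-specific SAP, not supplied, could supersede this text (Sections 1 and 6.5.1).

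Two stronger readings should be resisted. One is that the rule biases the comparison between arms: nothing in the documents suggests that losses at score 5 would differ by arm. The other is that a cut-off of 5 would give more accurate totals: under the assumed model it overcounts losses by Day 8 by more than row 4 undercounts them. The model is only illustrative, because its 53.6% comes from unpublished data on a mixed population. The case for the change is agreement with the endpoint definition and with the neighbouring rows. Severity: minor.

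**What to change.** In Table 7 row 4, change the carry-forward cut-off from 6 or above to 5 or above, and the stopping cut-off from below 6 to below 5. Add one sentence: a subject whose last status is a good discharge (not to LTAC, hospice or another hospital) gets no further imputed days unless the post-discharge oxygen form records oxygen.

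An alternative is to derive row 4 from the complete ordinal-score data, as rows 7 and 10 do, plus the oxygen days on that form. If the sponsor does intend to assume that patients last seen at score 5 come off oxygen, the SAP should say so and explain why row 4 differs from rows 5 and 8.

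In any of these cases, add a footnote to Table 36 giving the number of subjects with imputed days in each arm, so that readers can judge how much the rule matters.

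The cost is SAP wording only: two numbers, one sentence and one footnote, with no new data. The downside is that carrying oxygen to Day 29 will overcount some early losses, which the footnote makes visible.

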13. Days of hospitalization from date of admission by Study Day 29.	Primary	
 If a subject is discharged and no further hospitalization data are available, consider the subject as not readmitted, no additional imputed days will be added. If a subject dies while hospitalized, the number of days of hospitalization will be imputed as the number of days between the date of admission and the expected date of subject's Study Day 29 visit+1.
	Subgroup	
 Use complete data for ordinal score to define this endpoint.

Endpoint	Analysis	Imputation Method
Other Secondary Endpoints: Safety		
1. Values of CRP, ferritin, D-dimer, LDH, and fibrinogen on Study Day 1: Study Days 3, 5, 8, 11,15 and 29	Primary	
 If results are not available for any visit day(s) but are available for visits before or after that visit, the average of the two nearest visits will be imputed for all missing visits between them. If a subject dies or is otherwise terminated early from the study, their last available observation will be carried forward. If baseline is missing, another pre-treatment dose will be used, or the earliest post treatment dose will be used.
2. 14-day Mortality	Primary	
 Subjects whose last assessment in the study is before Day 13 (beginning of Day 29 window) and before death will be considered not dead and censored at the date of their last observed assessment. Subjects who complete follow-up will be censored at Day 15. Deaths that occur after Day 15 will be censored at Day 15.
	Primary with Sensitivity Imputation	
 Subjects whose last assessment in the study is before Day 13 (beginning of Day 15 window) and were discharged to a location other than LTAC, hospice care or other hospital, or subjects died after Day 15 will be considered non-events and censored at Day 15. Subjects whose last assessment in the study is before Day 13 (beginning of Day 15 window) and before death and without being discharged to a location other than LTAC, hospice care or other hospital at their last assessment will be considered non-events and censored at the date of their last observed assessment. Subjects who complete follow-up will be censored at Day 15.

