6.5.2. Multiple Imputation

Multiple imputation will be performed for the primary endpoint of the Day 8 ordinal score for subjects whose last assessment in the study is before Day 8 and missing ordinal scores after their last assessment for the following two scenarios:

- For the primary analysis of the primary endpoint, assign a score of 2 for subjects missing Day 8 score after last assessment for subjects with a good discharge status (i.e., discharged to a location other than LTAC, hospice care, other hospital) at last assessment and use multiple imputation to impute missing data at Day 8 only for subjects without a good discharge status (i.e., subjects with no post baseline data or still hospitalized or those discharged to LTAC, hospice care, or other hospital) at their last assessment

- As a sensitivity analysis of the primary endpoint, use multiple imputation to impute missing ordinal scores for all subjects missing Day 8 ordinal scores after last assessment regardless of their good discharge status at last assessment.

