The time to mechanical ventilation or death up to and including Day 29 will be defined as the elapsed time (in days) from Study Day 1 to date of mechanical ventilation or death. Any subjects whose last assessment is prior to obtaining the event and prior to Day 26 (beginning of Day 29 window) will be censored at the date of their last observed assessment. For the sensitivity analysis of this endpoint, subjects whose last assessment is

prior to obtaining the event and who were discharged to a location other than LTAC, hospice care, or other hospital will be considered recovered and censored at Day 29. For both primary and sensitivity analysis of this endpoint, subjects who complete follow-up will be censored Day 29. Events that occur after Day 29 will be censored at Day 29. A table will present median time to event along with corresponding 95% and 80% confidence intervals for each treatment along with the hazard ratio estimate and score test p-value from a Cox-proportional hazard model (Table 42). The Cox model will include as covariates baseline ordinal score, baseline CRP value, continuous age, and baseline dexamethasone use. Differences in time-to-event endpoints by treatment will be summarized with Kaplan-Meier curves (Figure 11). Analyses will be performed on the mITT population for those subjects who at baseline have an ordinal score of 5 or 6, CRP<150 mg/L, and age<85 years and results will be reported in Table 42. This analysis will be repeated for all subjects in the mITT population and results will be reported in Table 43.

Refer to Table 6 for a list of covariates and subgroup analyses for this endpoint. Refer to Table 7 for imputation methods to be applied to this endpoint.

Hospitalization

Duration (in days) of hospitalization will be defined as the number of days subject is hospitalized for COVID-19-related reasons starting from the date of randomization. It will be calculated as the total number of days hospitalized, including readmissions for COVID-19-related reasons. It will also be calculated as the total number of days hospitalized, including any readmissions regardless of cause. See Section 6.5 for the plan for handling subjects who do not have data through Day 29 or die prior to Day 29.

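### Hospital days (SAP Table 7, row 13): only in-hospital deaths count through Day 29, an untracked transfer counts as going home, and the primary and subgroup lines use different rules

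*SAP*

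**What the plan says.** SAP Section 4.5 takes hospital duration from admission and discharge dates. Section 8.2.2 (Hospitalization) counts readmission days and, for incomplete follow-up, directs: "See Section 6.5 for the plan for handling subjects who do not have data through Day 29 or die prior to Day 29". In Section 6.5.1 the relevant text is Table 7, row 13.

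- Primary line, discharge: "If a subject is discharged and no further hospitalization data are available, consider the subject as not readmitted", and no days are added. No destination is named.
- Primary line, death: "If a subject dies while hospitalized, the number of days of hospitalization will be imputed as the number of days between the date of admission" to the expected Day 29 visit, plus one day.
- Subgroup line: "Use complete data for ordinal score to define this endpoint". Section 6.5.1 builds that dataset by scoring death as 8, giving 2 after discharge to a location other than LTAC, hospice or another hospital, and carrying the last score forward for everyone else.

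Elsewhere the SAP separates good from other discharges. For the Day 8 primary endpoint, Section 6.5.2 names those without a good discharge status as "subjects with no post baseline data or still hospitalized or those discharged to LTAC, hospice care, or other hospital", and imputes their missing scores rather than assuming a good outcome.

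**The concern.** The death rule shows that the sponsor wants a death ranked with the longest stays and not the shortest. Tying it to place of death defeats that purpose for anyone discharged to hospice, or to any other place, who dies before Day 29. Separately, the SAP treats another hospital as a discharge location, so an untracked hospital-to-hospital transfer falls under the same rule as a discharge home.

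The direction is fixed: these poor or unknown outcomes are recorded as short stays. If the arms differ in hospice discharges or untracked transfers, the comparison of hospital days tilts toward the arm with more of them. Because the subgroup line follows another rule, subgroup results may also fail to reconcile with the overall result for the same endpoint.

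**Working it through.** The documents give no expected value, power or sample size for hospital days, so there is no figure to reproduce. The check applies the stated rules to example subjects.

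**Per-subject gap.** Let *a* be the days from admission to Study Day 1 and *d* the study day of discharge, with the discharge day counted.

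- Death in hospital (row 13): *a* + 28 + 1 = *a* + 29.
- Discharge with nothing added: *a* + (*d* − 1) + 1 = *a* + *d*.
- Gap: (*a* + 29) − (*a* + *d*) = 29 − *d*, so *a* cancels.

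For *d* = 6, 10 and 15 the gap is 23, 19 and 14 days. With *a* = 2 and *d* = 6, a hospice death on Day 9 is recorded as 2 + 6 = 8 days; the same death on the ward is 2 + 29 = 31 days.

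For the hospice death, this gap is exactly the difference between the two rules. For a transfer without later data it is an upper limit, because the subject may have gone home before Day 29.

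**The rules side by side.**

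| Subject | Row 13, primary | Row 13, subgroup |
|---|---|---|
| Dies on the ward, Day 9 | Through Day 29 | Score 8 from death |
| To hospice Day 6, dies Day 9, dates known | Ends Day 6 | Score 8 from death |
| Transferred to another hospital Day 6, no later data, last score a hospitalized one | Ends Day 6 | Hospitalized score carried to Day 29 |
| Withdraws Day 3 while ventilated | No rule | Score 7 carried to Day 29 |

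The subgroup line scores both deaths alike; the primary line does not. The subgroup line does not say whether a score of 8 counts as a hospital day. The oxygen and ventilation durations in Section 8.2.2 do count it.

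For the withdrawn subject, Table 7 row 8 also gives an answer ("then the subject will be considered to be on invasive mechanical ventilation/ECMO through Day 29"), so only the primary hospital-days line is left without one.

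**Figure 22.** Section 8.2.2 plots subjects whose days are imputed because of death apart from subjects who do not die. A hospice death belongs to neither group: the subject died, but no days were imputed.

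**Effect on the planned summary, on assumed data only.** Take stays that are lognormal with median 11 days and log-SD 0.83, rounded up and capped at 29 (about 13% at the cap). Move 2%, 5% or 10% of all subjects from the cap to stays of 5 to 10 days. The upper quartile falls from 20 to 19, 17 or 16. The median stays at 11 for 2% and falls from 12 to 10 for 5% and for 10%; the starting median sits on the edge between 11 and 12. None of these shares comes from the documents.

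**The case against.** Much can be said for the plan, and it rules out several stronger readings.

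- **That days always stop at transfer.** The discharge rule applies only when no further hospitalization data exist. Post-discharge contacts on Days 8, 15, 22 and 29 ask about readmission, Section 6.5.1 plans chart review for subjects lost to follow-up, readmission days are counted, and Protocol Section 5.2 excludes subjects with an anticipated transfer to a non-study hospital within 72 hours. Only untracked transfers are affected. This does not help the hospice death, where nothing is missing.
- **That days stop at in-hospital withdrawal.** No text says so. Without a discharge date the primary value is undefined, not short. Nor would ventilator days exceeding hospital days be an error in itself, since row 8's endpoint includes death.
- **That row 13 departs from a uniform SAP convention.** The good-discharge split is a primary rule only for the Day 8 score. For recovery, respiratory failure and mortality it appears only in sensitivity imputations, and the duration rows 4, 5 and 8 do not use it.
- **That a mean or the global test is distorted.** Section 8.2.2 plans medians and quartiles and names no test. Table 9 lists hospital days, but Section 6.8 makes those analyses optional, and the shells for Tables 44 and 45 omit the endpoint.
- **That hospice days are hospital days.** Days in home hospice are not, so a short stay is literally correct. The objection is to how it ranks beside an in-hospital death.

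The Master protocol sections on readmission and loss to follow-up are not among the documents, and a stage-specific SAP could change the rule. What remains is the text of row 13 itself.

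**Conclusion.** The point holds in this limited form. As written, the primary line gives the same death a short or a maximal stay according to where it occurs, counts an untracked transfer as a discharge home, and conflicts with the row's own subgroup line. It also leaves withdrawal while hospitalized unaddressed although Section 8.2.2 points to Section 6.5 for it. The endpoint review committee does not close the gap, since its remit in Section 6.5.1 is the primary and key secondary endpoints.

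The size is 23, 19 or 14 days per affected subject for exit on Day 6, 10 or 15, taking the in-hospital death rule (or continued hospitalization to Day 29) as the comparator. The number of affected subjects is unknown, so no effect on the arm-level result can be claimed. The primary endpoint is not touched.

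**What to change.** Rewrite Table 7 row 13 as one rule for both the primary and subgroup lines:

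1. Count any death by Day 29 through Day 29, regardless of place of death.
2. Add no days only after discharge to a location other than LTAC, hospice or another hospital.
3. For subjects last known in the study hospital or another hospital with no later data, including those who withdraw there, carry hospitalized status to Day 29. Use the receiving hospital's dates where they are known.
4. State whether days in LTAC or hospice count as hospital days for subjects not known to have died.

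In the same edit, settle the start of the count: SAP Section 3.2 and row 13 use admission, while Section 8.2.2 uses randomization.

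The cost is one SAP row plus matching programming. Discharge location is already collected and used elsewhere in Table 7. The downside is small: some transferred subjects who soon went home will be overcounted. With deaths counted through Day 29 the measure is partly a penalized duration, as it already is for in-hospital deaths, and the table footnote should say so.
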